## 6. STUDY PATIENTS

Unless otherwise specified, all tables in this section will be presented by the treatment regimen groups described in Section 5.1.1.

### 6.1. Disposition of Patients

Patient disposition will be presented by treatment regimen as described in Section 5.1.1.

This table will present the number and percentage of patients in the Safety Analysis Set and the All-Enrolled Analysis Set. Percentages will be based on the total number of patients who were enrolled in the study, or who received at least 1 dose of rFIXFc.

In addition, the number and percentage of patients in the Full Analysis Set (FAS) and in the FAS with an efficacy period, as well as those in the Surgery Subgroup, the Inhibitor Subgroups, and the ITI Subgroup, will be provided. The number and percentage of patients who completed/ discontinued the study, including the primary reason for those who discontinued, will be tabulated. Percentages will be based on the number of patients in the All-Enrolled Analysis Set.

Patient disposition, including the date of the last visit and the reason for early termination or early withdrawal for patients who did not complete the study, will be provided in a data listing.

The number and percentage of patients enrolled will be summarized by country and site, for the All-Enrolled Analysis Set.

The number of patients attending each key study visit will be summarized by key study visit overall for the Safety Analysis Set, including visits in the main study. If the ITI Subgroup consists of at least 5 patients, this summary will also be performed for the ITI Subgroup, including only visits in the ITI period.

### 6.2. Demography and Baseline Disease Characteristics

Demographics and baseline characteristics will be summarized for the Safety Analysis Set. Demographics and baseline characteristics will be summarized as continuous variables and as categorical variables, as appropriate.

#### 6.2.1. Demography

Demographic characteristics include age, height and weight at screening plus sex, race, ethnicity, and geographic location. Geographic locations are defined as Europe, North America, and other. Europe includes Belgium, Denmark, France, Germany, Ireland, Italy, the Netherlands, Poland, Spain, Sweden, Switzerland, and the United Kingdom. North America includes the United States. Other countries include Australia and New Zealand.

Age will be obtained from the interactive voice and web response system (IXRS) to avoid calculation errors arising from not having the day of the month for birth dates in the eCRF. Age will be summarized both as a continuous variable using descriptive statistics and categorically with the age categories representing each year from <1 through 17. This table will be presented by treatment regimen as described in Section 5.1.1.

	Statistical Analysis Plan	Final v1.0
---	----------------------------------	-------------------

### **6.2.1.1. General Medical and Surgical History**

Medical and surgical history will be summarized by body system. A patient is counted only once if they report more than one occurrence in the same body system.

### **6.2.2. Baseline Disease Characteristics**

#### **6.2.2.1. Hemophilia History**

Time since diagnosis of hemophilia will be summarized with descriptive statistics. The screening FIX activity values will be summarized categorically (<1%, ≥1%). Categorical summaries will also be provided for FIX genotype, family history of inhibitors, vaccination within last year, HIV status, Hepatitis B status, and Hepatitis C status.

#### **6.2.2.2. Bleeding History**

Patients' total estimated bleeding episodes (spontaneous plus traumatic) within the last 3 months prior to study screening will be summarized categorically (0, 1-2, 3-5 and >5 and with descriptive statistics). Percentages for the categorical summaries will be based on the number of patients who provided data. Total estimated bleeding episodes in the 3 months prior to study screening will also be summarized for the number of spontaneous and traumatic bleeding episodes using descriptive statistics.

#### **6.2.2.3. Family Hemophilia History**

No family history of hemophilia is collected in this study. Family history of inhibitors to FIX is referenced above in Section 6.2.2.1.

#### **6.2.2.4. Risk Factors for Inhibitor Development**

The following risk factors will be summarized for patients in the Inhibitor Subgroup and those not, as specified in Section 5.2.5:

- Race - black or African American or white Hispanic / other, from demography data
- Family history of inhibitor - Y/N, as per hemophilia history data
- Vaccination - Y/N, as per hemophilia history data and concomitant medications prior to date of inhibitor development
- FIX genotype - to be delineated based upon final data according to the following guidelines for all genotypes that fall under the general categories of:
  - High risk – large deletions or nonsense variants
  - Low risk – small deletions/insertions, missense variants, or promoter/regulatory region mutation
  - Unknown/missing
- TEAE of infection prior to date of inhibitor development - Y/N, derived from adverse event data based upon events with MedDRA SOC Infections and Infestations

	Statistical Analysis Plan	Final v1.0
---	----------------------------------	-------------------

- Major surgery during study prior to date of inhibitor development - Y/N

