#### 5.1.1. Data Presentation

In general, presentations of background/demography and safety data will include an overall/total column and those for efficacy and health outcome data will not. Any exceptions to this are specified in the relevant section.

There is only 1 treatment arm in the study. However, unless otherwise stated, all analyses and background/demography tables will be presented for the following treatment groups, as defined in Section 3.1.2:

- Patients who were ever on an episodic regimen
- Patients who were ever on a prophylactic regimen
- Patients who were ever on an ITI regimen

For longitudinal data, the safety or efficacy periods included for these groups is the time spent on that regimen within that period. These periods are defined in Section 5.3 and 5.4.

Selected tables will also be presented by patients’ inhibitor development status, if there are at least 5 patients in the positive inhibitor subgroup (defined as in Section 5.2.4).

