**High and Low Titer Positive Inhibitors**

A positive inhibitor test result is defined as an inhibitor test result of  $\geq 0.60$  BU/mL that is confirmed by a second test result of  $\geq 0.60$  BU/mL from a separate sample, drawn 2 to 4 weeks following the original sample. Both tests must be performed by the central laboratory using the Nijmegen-modified Bethesda assay. The date of the inhibitor is the date of the sample with the first positive test result which was subsequently confirmed.

- A positive low titer inhibitor is defined as an inhibitor test and confirmatory test, both with results of  $\geq 0.60$  and  $< 5.00$  BU/mL.
- A positive high titer inhibitor is defined as an inhibitor test and confirmatory test, both with results of  $\geq 5.00$  BU/mL.

Patients with discordant inhibitor test results (initial low titer result followed by high titer result or initial high titer result followed by low titer result) should have repeat inhibitor testing performed by the central laboratory from a third separate sample, drawn 2 to 4 weeks following the previous sample.

- If 2 of 3 test results are  $< 5.00$  BU/mL, the inhibitor is considered low titer.
- If 2 of 3 test results are  $\geq 5.00$  BU/mL, the inhibitor is considered high titer.

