### 9.3.1. Treatment-emergent Adverse Events

An AE will be regarded as treatment-emergent if it was present prior to receiving the first injection of rFIXFc and subsequently worsened in severity, or was not present prior to receiving the first injection but subsequently appeared before the patient’s last visit on study or the follow-up phone call, whichever came later (or the date of withdrawal/loss to follow-up).

The algorithm for the determination of treatment emergence when an onset date is partially or completely missing is described below.

- If the onset time of an adverse event (if time is collected) is missing and the date of onset is the date of dosing, the AE is considered to be a TEAE.
- If the onset day of an adverse event is missing and the month and year of the onset of the AE are either the same or later than the month and year of the first treatment, the AE will be considered a TEAE.
- If the onset day of an adverse event is missing and the month and year of the onset of the AE precede the month and year of the first treatment, the AE will not be considered a TEAE.
- If the onset month of an adverse event is missing and the year of the onset of the AE is either the same as or later than the year of first treatment, then the AE will be considered a TEAE.
- If the onset month of an adverse event is missing and the year of AE onset precedes the year of first treatment, the AE will not be considered a TEAE.
- If the onset day, month, and year of an adverse event are missing, the AE will be considered to be a TEAE.
- If start date is partial but the stop date can be determined to be before the start of the first dose of study drug, then the AE will not be considered a TEAE.

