## **Time to Inhibitor Development**

The cumulative incidence of inhibitors over time (EDs) will be estimated using the Kaplan-Meier method. For patients who do not have an inhibitor, follow-up time will be censored at the last ED at the time of analysis. This will be presented graphically for high and low titer (CS and NCS) inhibitors and overall, if at least 5 patients develop positive inhibitor.

Additionally a summary of EDs at time of inhibitor development will be provided, again for high and low titer (CS and NCS) inhibitors and overall. This will include Kaplan-Meier estimates of cumulative incidence of inhibitor development at 10, 20 and 50 EDs.

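### The inhibitor risk-factor table stops counting infection, major surgery and on-study vaccination at the inhibitor date, but sets no cut-off for patients who never develop an inhibitor.

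*SAP*

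**What the plan says.** SAP 6.2.2.4 opens with "The following risk factors will be summarized for patients in the Inhibitor Subgroup and those not". Three of the listed factors accrue during the study, and each ends at the inhibitor date:

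- infection: "TEAE of infection prior to date of inhibitor development - Y/N, derived from adverse event data";
- vaccination: "Vaccination - Y/N, as per hemophilia history data and concomitant medications prior to date of inhibitor development";
- surgery: "Major surgery during study prior to date of inhibitor development - Y/N".

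SAP 5.2.4 fixes the date: "The date of the inhibitor is the date of the sample with the first positive test result which was subsequently confirmed". It therefore exists only for patients with a confirmed inhibitor. No replacement date, ED count or censoring point for the others appears in 6.2.2.4, in the subgroup definitions (5.2.5), in the list of changes (Section 10) or in the table list (Section 12).

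Two general rules give an outer limit. SAP 9.3.1 lets treatment-emergent events run to the patient's "last visit on study or the follow-up phone call, whichever came later". SAP 6.4.1 excludes only concomitant medications that start after the follow-up visit. The SAP does set an end of follow-up for non-cases in the time-to-inhibitor analysis in 9.4.3.3, "For patients who do not have an inhibitor, follow-up time will be censored at the last ED at the time of analysis", but 6.2.2.4 does not refer to it.

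**The concern.** A Yes/No row answers whether the event happened at least once, so its percentage rises with the length of the window. Giving one group a shorter window lowers its percentage with no difference in risk. Here the window for cases closes when the inhibitor appears, and the window for non-cases is left open. The natural default is the general safety window, which lasts until they leave the study.

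Inhibitor development is the primary endpoint, and this is the planned table that sets these exposures beside it. A reader who sees infection in a smaller share of inhibitor patients could conclude that infection is unrelated to inhibitors or even protective, when only the counting windows differ.

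**Working it through.** The plan gives no figure on this point, so there is nothing to reproduce. The check is how far unequal windows alone move the infection row.

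**Inputs from the documents.** Recommended starting prophylaxis is weekly (Protocol 7.3.2), so about 1 ED per week. A patient not on immune tolerance induction completes at 50 EDs or more (Protocol 10.6; SAP 5.2.3). ED 10 and ED 20 are milestones in SAP 9.4.3.3. An episodic phase of investigator-chosen length may come first (Protocol 7.3.2 and 10.2.2.1).

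**Assumptions.** A constant rate r = 1 infection per year, equal in both groups; inhibitor at ED 10 or ED 20; non-cases counted for 50 EDs; an episodic phase adding 0, 26 or 52 weeks to both windows.

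**Formula.** P(yes) = 1 − exp(−r × w/52), with w in weeks. The odds ratio (OR) is the odds in cases divided by the odds in non-cases. For ED 10 with weekly dosing:

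- cases: 1 − exp(−10/52) = 0.175, odds 0.212;
- non-cases: 1 − exp(−50/52) = 0.618, odds 1.616;
- OR = 0.212/1.616 = 0.13.

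| Weeks added to both | Inhibitor at | Windows, cases vs non-cases (weeks) | Yes, cases vs non-cases | OR |
|---|---|---|---|---|
| 0 | ED 10 | 10 vs 50 | 17% vs 62% | 0.13 |
| 0 | ED 20 | 20 vs 50 | 32% vs 62% | 0.29 |
| 26 | ED 10 | 36 vs 76 | 50% vs 77% | 0.30 |
| 26 | ED 20 | 46 vs 76 | 59% vs 77% | 0.43 |
| 52 | ED 10 | 62 vs 102 | 70% vs 86% | 0.38 |
| 52 | ED 20 | 72 vs 102 | 75% vs 86% | 0.49 |

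With equal windows every OR would be 1.00. Early leavers also narrow the gap: for non-cases followed 25 weeks under weekly dosing, P = 1 − exp(−25/52) = 0.382, and the OR is 0.34 (ED 10) or 0.76 (ED 20).

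**A real association.** Suppose cases truly have twice the rate (2 vs 1 per year) and the inhibitor appears at ED 10.

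- Weekly dosing: 1 − exp(−20/52) = 32% in cases against 62%, OR 0.29. On equal 10-week windows it would be 32% against 17%, OR 2.21.
- With 26 weeks added: 1 − exp(−72/52) = 75% against 77%, OR 0.90. On equal 36-week windows it would be 75% against 50%, OR 3.00.

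**The other coding.** If a missing inhibitor date is taken to mean that nothing can precede it, every non-case is No for infection and surgery. Non-cases then show 0%, and any event in a case looks like an excess.

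**The case against.** The strongest reply is that little depends on this table. It is descriptive and sits under baseline characteristics. The primary proportion with its Clopper-Pearson interval, the ED-milestone incidence and the Kaplan-Meier analysis do not use it. Race, family history and genotype do not change over time and are unaffected; genotype is the risk factor that the protocol's stopping rule gives as its example. SAP 5.1.1 restricts selected tables by inhibitor status to the case "if there are at least 5 patients in the positive inhibitor subgroup". It does not name the tables, but this one is a natural candidate. All of that stands and limits the importance.

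Next, 5 cases could not establish an association under any window: the exact 95% interval for 1 of 5 is 0.5% to 72%. That also stands, but a systematic shift in one direction is a separate fault from imprecision and is cheap to remove.

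Third, major surgery should involve few patients, and the vaccination row is diluted by baseline history. This is accepted; infection is the row that matters. Adverse event listings with onset days, and a planned risk-factor listing, also let a careful reader rebuild the timing. They do not correct the summary.

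Finally, table shells and programming specifications are not available and may hold a rule. A reader might infer that the SAP instructs whole-study counting for non-cases. It does not: that reading follows from the general adverse event and medication windows, and the text would equally allow coding non-cases as No.

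**Conclusion.** The gap in the SAP text is real. As written, the three rows do not give the two groups comparable windows under either plausible reading. Under whole-study counting, the exposures look too rare in cases as long as inhibitors generally arise before non-cases end follow-up. Under No-coding the error runs the other way.

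Its size cannot be fixed from the documents. At the assumed 1 infection per year, with non-cases reaching 50 EDs, the spurious odds ratio lies between 0.13 and 0.49 over the scenarios tabulated. It would be tempting to quote only 0.13 and 0.29, but those need weekly dosing from the first dose, and the protocol allows an open-ended episodic phase. It would also go too far to say that the table must reverse a real association: in the doubled-rate example it does so with weekly dosing but mostly hides it once 26 weeks are added. Nor does anything here weaken the primary inhibitor analysis. Importance is minor to modest, and mainly for the infection row.

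**What to change.** State in SAP 6.2.2.4 one at-risk window that applies to both groups for infection and for the concomitant-medication part of vaccination. Either form would do:

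- **Same-ED comparison.** Compare each case at its inhibitor ED with patients still inhibitor-free and under follow-up at that ED, counting exposures up to that ED in both. This keeps a Yes/No display and needs no constant rate. It aligns EDs rather than calendar time, so time on study at that ED should be shown.
- **Counts and patient-years.** Report events and patient-years from first dose to the inhibitor date (cases) or last ED (non-cases, the censoring rule already in 9.4.3.3). Rates assume a roughly constant risk and will be imprecise. Five cases at week 10 give 5 × 10/52 = 0.96 patient-years, so 1 event is 1.04 per year with exact 95% interval 0.03 to 5.8. Counts must therefore stand beside the rates.

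For major surgery, a listing with timing is enough. Race, family history and genotype stay as they are. The SAP should also say whether the 5-patient condition in 5.1.1 covers this table.

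The cost is a few sentences of SAP text, a little programming from onset days already planned for the listings, and a slightly less simple table. No new data are needed and no endpoint changes.

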### 6.3. Physical Examination

The number and percentage of patients with physical examination abnormalities at screening will be presented by body system. Percentages will be based on the number of patients for whom a screening physical examination is available. On-treatment physical examination findings will be listed.

### 6.4. Non-study Drug Medications

#### 6.4.1. Prior and Concomitant Medications

Prior and concomitant medications relative to rFIXFc will be summarized for the Safety Analysis Set. Summaries will be based on the number and percentage of patients taking medications by WHODrug standardized medication text. Within each WHODrug standardized medication text a patient will be counted once even if he reported taking the medication more than once. Separate summaries will be provided for prior and concomitant medications. Medications taken after the EOS visit up to the Follow-Up visit/phone call will not be included in the summary table of concomitant medications. Two listings will be provided, one for prior and concomitant medications taken through the EOS visit and the other for medications taken after the EOS visit and prior to the Follow-Up visit/phone call.

Medications will be identified as being prior and/or concomitant based on the start and stop dates compared to the first dose of rFIXFc. Prior medications are all drugs and substances taken before the first rFIXFc dose was received. Concomitant medications are those administered during or after the first injection of rFIXFc while on study, or administered prior to the first administration of rFIXFc and ongoing at the start of rFIXFc administration.

Prior and concomitant medications will be characterized based on the onset and resolution dates relative to the date and time of the first dose of rFIXFc. Medications reported for a patient will be classified as concomitant unless they can be excluded as such, as follows:

- A medication that is started prior to the first dose of rFIXFc and was ongoing during and/or after the first dose of rFIXFc will be classified as both prior and concomitant.
- Medications with a start date after the follow-up visit will not be considered concomitant and will not be included in the summary tables.
- For partial dates, if a concomitant medication start day is missing then the medication will be assumed to be both a prior and a concomitant medication unless the start month and/or year or medication stop date can be used to determine if a medication is concomitant or prior, as follows:
  - If the concomitant medication start day is missing, but the month and year are before the start month and year of the first dose of rFIXFc and the concomitant medication stop date is before the start day of the first dose of rFIXFc, then the medication will be classed as prior only.

	Statistical Analysis Plan	Final v1.0
---	----------------------------------	-------------------

- If the day of the start date is missing and the month and year are after the month and year of the first dose of rFIXFc then the medication will be classed as concomitant only.
- If the month of the start date is missing and the year is before the start year of the first dose of rFIXFc and the stop date is before the start date of the first dose of rFIXFc, then the medication will be classed as prior only.

In this study, for patients who receive breast milk, maternal concomitant medications are also collected at the same time points as other concomitant therapies, unless the breast milk is derived from a source other than the mother or the mother did not consent. These will be presented in separate listings, but in a similar way, to other concomitant medications.

Prior and concomitant medication will be coded using WHODrug-enhanced dictionary version from March 2017.

#### **6.4.2. Other Therapies and Procedures**

Other therapies administered and concomitant procedures performed within 30 days prior to the first dose of study drug through the end of the study will be listed only, a summary table is not planned.

#### **6.5. Protocol Deviations**

Protocol deviations will be recorded throughout the study or in the case of deviations based upon data entered in the EPD, monitored throughout the study and finalized at the end (more details in the Programmatically-Defined Protocol Deviations Criteria document). Major and minor protocol deviations/violations are to be pre-specified prior to database lock, as per the guidance provided in the study Clinical Operations Plan document.

The number of patients with major protocol deviations will be summarized for the Safety Analysis Set and also including only deviations that affect efficacy, to be identified prior to database lock. Major protocol deviations that occurred during a surgical/rehabilitation period will be presented separately in the summary. A data listing of all protocol deviations, major and minor, will be provided.

#### **6.6. Study Drug**

Study treatment is described in Section 3.1.2. Study drug administered will be listed by patient for the FAS. This will include the reason for administration (PK assessment, episodic (treatment of a bleeding episode), prophylaxis, ITI, surgery, other), date and time of administration, dose and dosing intervals, consumption and compliance. It will also include lot number and nominal potency of the lots used.

Except for PK doses, the unit body weight dose (IU/kg) for analysis of dosing will be calculated as the total IU (nominal dose) for each injection divided by the patient’s most recent weight in kg prior to the dose of study drug.

PK doses are all 50 IU/kg at the Baseline IR Visit and the ITI regimen IR assessments, and are calculated using the actual potency of the vial (between 80 to 125% of nominal strength) and using partial vials where necessary. Therefore PK doses in the analysis are similarly calculated using the exact number of complete and partial vials, the volume and actual potency of each vial and the patient’s most recent weight.

Both types of dose are calculated as follows:

$$\text{Dose (IU/kg)} = \frac{\left( \frac{\text{Total volume administered}}{\text{Volume of vial}} \right) \times \text{Actual/Nominal Potency of Vial}}{\text{Weight (kg)}}$$

PK doses are not used for the purpose of preventing or treating bleeding and therefore the total annualized rFIXFc consumption will exclude the IU/kg amount that is used for PK doses. However, data collected over the time in which the PK dose was administered will be included in the safety analyses.

